#### BENEFITS

Subjects will not derive direct benefit from this study.

#### COST

There is no cost to subjects to participate in this study.

TITLE OF PROJECT: On-Demand PEP  
Emory IRB  
PRINCIPAL INVESTIGATOR: [name], MPH

### ALTERNATIVE

The alternative to participating in this study is to decide not to participate. Subjects can withdraw their consent at any time.

### COMPENSATION

All participants will be compensated for their time and inconvenience of study participation. Compensation will be provided on a web-based, reloadable, debit card (ClinCard) that automates reimbursements. The ClinCard will be provided by study staff at the participants' initial visit (visit 1), and funds will be loaded after the completion of each visit.

For Pre-drug Arm, study participants will be compensated \$25 for visit 1 and \$125 for visit 2. Participants who enter into Arm A, Arm B, and Arm C will be compensated \$25 for visit 1, \$20 for visit 2, \$20 for visit 3, and \$50 for visits that include swab collections in addition to blood and urine, and \$125 for visits in which a rectal biopsy procedure is performed. Participants in Arm D will be compensated \$25 for visit 1, \$20 for visit 2, \$20 for visit 3, and \$125 for visits in which a rectal biopsy procedure is performed.

If a semen sample is provided, participants will be compensated an additional \$20.

If a contingency visit is necessary, participants will be compensated \$20 for completion of a contingency study visit.

There is no charge for parking at the Hope Clinic. However, participants may be provided with a MARTA card if available.

### PLAN FOR OBTAINING INFORMED CONSENT

After being screened for eligibility by the PI or study coordinator, subjects will be informed about the study and asked to sign an Emory IRB approved informed consent. The consent form will describe the purpose of the study, the procedures to be followed, and the risks and benefits of participation. Subjects will be consented in a private exam room. Subjects will be given time to read the consent, ask questions and consider the risks and/or benefits to participation in this research study prior to obtaining their signature. All subjects enrolled in the study will be given a copy of their signed and dated informed consent document. This consenting process will be done by trained research staff at the Hope Clinic. All subjects will undergo HIV risk reduction counseling with provision of free condoms.

### PROVISIONS FOR SUBJECTS FROM VULNERABLE POPULATIONS

Non-English speaking subjects or illiterate subjects will not be eligible to participate in this study.

TITLE OF PROJECT: On-Demand PEP  
Emory IRB  
PRINCIPAL INVESTIGATOR: [name], MPH

#### PARTICIPATION OF WOMEN AND CHILDREN

Because this is a study of MSM, women are not eligible. Children 18-21 will be eligible for this study. It is especially important to include MSM aged 18-21 as young MSM are at highest risk of HIV infection and research that may lead to better prevention interventions, including an HIV vaccine, are desperately needed for this group. Children younger than 18 will not be eligible.

#### SUBJECT PRIVACY AND DATA CONFIDENTIALITY

All subjects will provide informed consent in a private room at the Hope Clinic.

Case report forms (CRFs) will be provided for each subject to collect demographic, behavioral, clinical, and laboratory data at study entry, and additional clinical data at the study visit. These data will be collected from the screening clinical assessment, the study entry physical examination and screening laboratory tests, and rectal biopsy visits. Subjects will be identified by the participant identification number (PID), which will be provided by the study investigator upon registration. All laboratory specimens, evaluation forms, reports, and other records that leave the site will be identified by coded number only to maintain subject confidentiality. All study samples will be kept in a secure area in a limited-access laboratory facility and only the research team will have access to the samples. The samples and data will be identified only by code numbers.

Any identifiable records will be kept locked accessible only by authorized study personnel. Electronic data will be password protected and stored on the Redcap server or the Emory School of Medicine HIPAA compliant server. Biologic samples will be coded with a unique identifier and no identifiable behavioral data will be shared with laboratory investigators at CDC. Information about the subject's participation will not be shared with individuals who are not directly involved with the research subjects. Clinical information will not be released without written permission of the subject, except as necessary for monitoring by IRB, the FDA, the NIH, or the OHRP. Information about the subject's participation will not be shared with individuals who are not directly involved with the research subjects.

#### PLANS FOR SUBJECTS AT THE END OF THE PROTOCOL

Subjects will return to the standard of care at the end of the protocol. Subjects who are interested in starting PrEP will be linked to care with a community provider. In the event that study staff needs additional information, after enrollment is complete, or has additional questions pertaining to study analysis, staff will obtain consent from participant for future contact.

TITLE OF PROJECT: On-Demand PEP  
Emory IRB  
PRINCIPAL INVESTIGATOR: [name], MPH

### CLINICAL SITE MONITORING AND RECORD AVAILABILITY

The Emory University IRB, the OHRP, FDA, or other government regulatory authorities may perform clinical site monitoring. Clinical research sites monitoring may include the review of the individual participant records, including consent forms, CRFs, supporting data, laboratory specimen records, and medical records (physicians' progress notes, nurses' notes, individuals' hospital charts) to ensure protection of study participants, compliance with the protocol, and accuracy and completeness of records. The monitors may also inspect sites' regulatory files to ensure that regulatory requirements are being followed.

The investigators will make study documents (e.g., consent forms, CRFs) and pertinent hospital or clinic records readily available for inspection by the local IRB or the OHRP for confirmation of the study data.

### ADVERSE EVENT MONITORING AND REPORTING

Adverse events (AEs)  $\geq$  Grade 3 will be reported on an expedited basis at the standard level during the protocol-defined expedited adverse event (EAE) Reporting Period, which is the entire study duration for an individual subject (from study enrollment until study completion or discontinuation of the subject from study participation for any reason).

This study uses FDA approved drugs with known common side effects (please refer to the risk section of the protocol for common side effects). The following side effects will not be reported as an AE unless it increases in severity or becomes prolonged beyond the two day study follow-up period after final biopsy/ procedure visit.

Nausea: Report if severity is a Grade 3 or higher

Vomiting: Report if severity is a grade 3 or higher

Diarrhea: Report if severity is a Grade 3 or higher

Headache: Report if severity is a Grade 3 or higher

Rash: Report if severity is a Grade 3 or higher

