### STUDY POPULATION

A total of up to 62 HIV-negative MSM aged 18-49 will be recruited from existing Emory University study databases of MSM who have agreed to future contact about research opportunities. We will also recruit men from community engagement events conducted by Hope Clinic recruiters, from print and on-line advertisements, and from social media. Research recruiters at the Hope Clinic are experienced in recruiting this population for research studies, including those with rectal biopsies, and do not anticipate problems. [name] has conducted several similar studies before and does not anticipate any problems with recruiting the target population. Based on our previous studies, we expect a percentage of men will not complete all study visits, therefore the sample size of up to 62 men will likely result in study completion for 31 men.

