All rectal biopsies will be performed utilizing a disposable rigid sigmoidoscope, light source, and jumbo biopsy forceps. [name] was trained in office based rectal biopsy procedures by [name], an experienced gastroenterologist at Emory University. All biopsies will be completed by either the PI or a delegated, licensed medical professional whom the PI has trained in the procedure. All biopsy procedures will be performed in an examination room at the Hope Clinic with assistance from the project coordinator or clinical research nurse. Similar procedures have been performed by [name] >300 times for other research protocols with no complications. Briefly, without the administration of any previous enemas or other preparation, 8-10 adequate ~1.0 mm thick biopsy specimens will be taken from normal-appearing rectal mucosa 10 cm above the external anal aperture using a rigid sigmoidoscope and flexible sigmoidoscopic forceps mounted on a semi-flexible rod. All biopsy specimens will be coded with a unique numeric identifier such that the CDC laboratories that receive the

TITLE OF PROJECT: On-Demand PEP  
Emory IRB  
PRINCIPAL INVESTIGATOR: [name], MPH

specimens will be unable to link them back to the study participants. Specimens will be transported directly to CDC after the study visit.

Twenty-four to forty-eight hours after the procedure, study personnel will contact the subjects who donated rectal biopsy samples and inquire about symptoms, complications, or adverse events related to study procedures. Subjects who report symptoms suggestive of any significant complications will receive advice on seeking care, and will be given referrals to appropriate healthcare professionals as needed. This follow-up may be completed over the phone or through electronic communication.

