#### AE Reporting

Any AE that is reported to either the investigators or their designated research associates by a study subject or by medical staff caring for the subject and which meets the criteria will be documented.

In addition, clinical investigators will monitor subjects for Serious adverse events (SAE) Unanticipated problems (UP) during each study visit. Any SAE that is judge related to study product or UP will be reported to the IRB within 5 days of the event. The standard Emory IRB reporting guidelines for AE and SAE reporting, as documented at [http://www.emory.edu/IRB/guidelines\\_adverse\\_event.php](http://www.emory.edu/IRB/guidelines_adverse_event.php), will be followed.

A SAE is an adverse drug experience that results in any of the following outcomes:

1. Death.
2. Life-threatening situation - The subject was at risk of death at the time of the adverse event/experience. It does not refer to the hypothetical risk of death if the AE were more severe or were to progress.
3. Inpatient hospitalization or prolongation of existing hospitalization.
4. Persistent or significant disability/incapacity - Any AE having an outcome that is associated with a substantial disruption of the ability to carry out normal life functions, including the ability to work. This is not intended to include transient interruption of daily activities.
5. Congenital anomaly/birth defects - Any structural abnormality in subject's offspring that occurs after intrauterine exposure to treatment.
6. Important medical events/experiences that may not result in death, be life-threatening, or require hospitalization may be considered a serious adverse event/experience when, based upon appropriate medical judgment, they may jeopardize the subject and may require medical or surgical intervention to prevent one of the outcomes listed above, i.e., death, a life-threatening adverse event/experience, inpatient hospitalization or prolongation of existing hospitalization, a persistent or significant disability/incapacity, or a congenital anomaly/birth defect. Examples of such medical events/experiences include allergic bronchospasm requiring intensive treatment in an emergency room or at home, blood dyscrasias or convulsions that do not result in inpatient hospitalization, or the development of drug dependency or drug abuse.
7. Spontaneous and elective abortions will be reported to the Emory IRB as serious adverse events.

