### DATA SAFETY MONITORING

Summaries of adverse events (Grades 3 or 4), and targeted AEs across study groups as well as study conduct will be reviewed regularly (in real time and summarized quarterly) by study investigators. Any SAE that is judged related to study product or UP will be reported to the IRB within 5 days of the event. The standard Emory IRB reporting guidelines for AE and SAE reporting, as documented at [http://www.emory.edu/IRB/guidelines\\_adverse\\_event.php](http://www.emory.edu/IRB/guidelines_adverse_event.php), will be followed.

Additional safety monitoring will be performed annually by an independent Medical Safety Monitor. Based on the 1 year accrual expectation for the study, it is anticipated that the study will undergo 2 reviews by the Medical Safety Monitor. The first will occur approximately 6 months after the accrual of the first subject. The safety report will summarize AEs and SAEs by study group. The Medical Safety Monitor will complete a 'final assessment' following the review of each safety report. As part of the final assessment the Medical Safety Monitor will conclude 'the study can continue as no safety concerns have been identified at the time of the review' or 'the study cannot continue as currently designed'. The final assessment by the Medical Safety Monitor will be provided to the study PI who will make the findings available as appropriate to the Emory IRB and the CDC.

In addition to the medical monitor, we will also conduct site monitoring for data quality and protocol compliance. The PI and the research coordinators will monitor for protocol compliance and data quality with periodic quality monitoring checks. In addition, we will perform self-monitoring twice yearly using the EU-Self-monitoring Tool available at [http://www.ctac.emory.edu/clinical\\_trial\\_resources/Audit%20Tools.html](http://www.ctac.emory.edu/clinical_trial_resources/Audit%20Tools.html). The PI will inform the sub-investigators and the IRB if she is provided with new safety information about the study.

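### No safety contact is scheduled for men who take at least one dose and stop before their biopsy, so later events in them depend on passive reporting

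*Combined protocol and SAP*

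**What the plan says.** Five parts of the protocol bear on who is followed for safety, and for how long.

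- **Adverse Event Monitoring and Reporting.** Adverse events of Grade 3 or higher "will be reported on an expedited basis at the standard level during the protocol-defined expedited adverse event (EAE) Reporting Period", which is defined as running "from study enrollment until study completion or discontinuation of the subject from study participation for any reason". The same section lists five common side effects (nausea, vomiting, diarrhea, headache, rash). These are not reported unless they worsen or outlast a "two day study follow-up period after final biopsy/ procedure visit".
- **Rectal biopsy procedures.** At 24 to 48 hours post-biopsy, "study personnel will contact the subjects who donated rectal biopsy samples and inquire about symptoms, complications, or adverse events related to study procedures". The contact may be by phone or electronic.
- **AE Reporting.** During the study "clinical investigators will monitor subjects for Serious adverse events (SAE) Unanticipated problems (UP) during each study visit". Separately, "Any AE that is reported to either the investigators or their designated research associates by a study subject or by medical staff" is documented if it meets the criteria. That sentence has no end date.
- **Study Population.** Losses are expected, "therefore the sample size of up to 62 men will likely result in study completion for 31 men".
- **Data Safety Monitoring.** For the independent Medical Safety Monitor, "The safety report will summarize AEs and SAEs by study group". The monitor then concludes whether the study can continue as designed.

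The retention calls, texts and emails described under Study visits take place while a man is on study. Their stated purpose is retention and adherence, and no safety content is given.

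**The concern.** Active safety ascertainment is tied to attending a visit or giving a biopsy. A man who has been exposed to drug and then leaves gets neither. The protocol itself plans for about half of enrolled men not to complete, so this is a foreseeable group.

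The first dose makes the gap wider. It is taken at home, and the photo or video is brought to the next visit, with a text message as the alternative when the phone cannot record. If a man does not come back for visit 3, the study may not know whether he was exposed at all. The number of dosed men, which any adverse event rate needs as its denominator, is then uncertain.

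The primary purpose is pharmacokinetic, so no efficacy or concentration result is at risk. What is at stake is the completeness of the safety report. Each drug group closes at four biopsies, so a single event that nobody asked about is large relative to its group.

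**Working it through.** **1. Reproduce the protocol's figures.** The enrolment caps and completion targets come from the arm descriptions under Study visits.

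- Caps: 6 (pre-drug) + 16 (A) + 16 (B) + 16 (C) + 8 (D) = 62.
- Completion targets: 3 + 8 + 8 + 8 + 4 = 31.
- Expected completion: 31 / 62 = 50%.

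Both stated figures reproduce exactly.

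**2. Restrict to men who receive drug.** The pre-drug arm gets none.

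- Places: 62 − 6 = 56.
- Planned completers: 31 − 3 = 28.
- Non-completers if every group fills to its cap: 56 − 28 = 28.

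**3. Trace what a man receives according to the last visit he attends.**

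| Last visit attended | Doses taken | Groups | Last visit-based check | 24 to 48 h contact |
|---|---|---|---|---|
| Visit 2 | 0, or 1 at home (may be unverified) | All drug groups | None after a dose | No |
| Visit 3 | 2 | All drug groups | 24 h after dose 1; none after dose 2 | No |
| Visit 4 | 2 | A.2, B.2, C.2 | 2, 4 or 24 h after dose 2 | No |
| Visit 4 | 2 | A.1, B.1, C.1 | 2, 4 or 24 h after dose 2 | Yes, procedure effects only |
| Visit 4 | 2 | D | 8 h after dose 2 | Yes, procedure effects only |

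The gap is in the first three rows: men who stop after a dose and before their biopsy. Men in A.1, B.1 and C.1 who miss only visit 5 count as non-completers but still get the contact. In Arm D, visit 4 is the last visit.

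**4. Bound the number affected.** Let f be the share of the 28 non-completers who took a dose and stopped before biopsy. The documents do not give f, so the whole range is shown. Affected men = 28f, and their share of all dosed men = 28f / (28 + 28f).

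| f (assumed) | Affected men | All dosed men | Share |
|---|---|---|---|
| 0 | 0 | 28 | 0% |
| 0.25 | 7 | 35 | 20% |
| 0.5 | 14 | 42 | 33% |
| 0.75 | 21 | 49 | 43% |
| 1 | 28 | 56 | 50% |

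The upper end is loose for four reasons. Consent is at visit 1 and drug is first supplied 1 to 6 weeks later, so some losses precede any dose. Men may enter more than one arm, so 56 places need not be 56 men. Some non-completers have already had their biopsy (step 3). And a group closes once four men complete their biopsy, so the caps may not be reached.

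**5. Set the two follow-up periods side by side.** The two-day period for common side effects starts at the final biopsy or procedure visit. A man who stops before any such visit has no starting point for it. For a man whose final visit is a collection without biopsy, no contact is described that would cover it. The only contact described is the one for biopsy donors. These passages do not fit together as written.

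**The case against.** The strongest reply is that the safety net is wider than the quoted period suggests, and much of that reply stands.

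- The period that closes at discontinuation governs expedited reporting of Grade 3 or higher events only. Events volunteered by the man or by treating staff are documented with no stated end date, and related serious events go to the IRB within 5 days.
- An event that leads a man to leave begins before he leaves, so its onset falls inside even the expedited period.
- The safety report is by study group, and nothing restricts it to completers or biopsied men.
- A man who took both doses was seen at visit 3, 24 hours after the first.
- The drug is approved and limited to two doses, and no tolerability endpoint is planned.

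A reader might therefore be tempted to infer too much: that dosed drop-outs are absent from the safety record, or that tolerability is overstated by a calculable amount. The documents support neither. They give no reasons for non-completion, no event rate and no count of dosed drop-outs. One could assume a true event rate of 10% and 42 dosed men, with men who have the event twice as likely to leave. The rate among the 28 who stay would then be 5.9%. But this requires 61% of men with the event to leave before biopsy and none of those events to be captured. If leaving is unrelated to events, the rate stays at 10%. Such a calculation also treats the 24 to 48 hour contact as deciding who is observed for drug effects, although that contact does not ask about them.

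None of this supplies the missing contact. Visit-based monitoring stops when attendance stops, and volunteered reports are passive.

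**Conclusion.** The point holds in this form: no scheduled safety contact exists for a man who takes at least one dose and stops before biopsy, and the expedited period for Grade 3 or higher events closes when he discontinues. Events that appear after he stops attending depend on passive reporting.

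The number of such men is between 0 and 28, with 28 a loose ceiling. It rests on every drug group filling to its cap, every non-completer having been dosed, none having reached biopsy, and no man taking more than one place. No direction or size of bias in an event rate can be derived from the documents. If leaving is unrelated to events, the loss is only of information.

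This is a weakness in safety ascertainment and does not threaten the pharmacokinetic objective. It is worth correcting because the losses are planned for, the groups are very small, and the Medical Safety Monitor's conclusion rests on these reports.

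**What to change.** 1. **Rectal biopsy procedures.** Extend the existing phone or electronic contact to every man who was dosed, or may have taken the home dose, and did not reach biopsy, subject to his continued willingness to be contacted. Ask all contacted men about drug effects as well as procedure effects. For men who missed visit 3, also record whether the home dose was taken.
2. **Adverse Event Monitoring and Reporting.** Reconcile the expedited reporting period and the two-day follow-up period with the biopsy-donor contact, so that an event after the last dose or procedure is not outside the reporting period merely because the man has discontinued. The length of the period is for the sponsor and investigator to set.
3. **Data Safety Monitoring.** In the safety report, give adverse events and serious adverse events by group over all men who took at least one dose, with the number reached and not reached after the last dose.

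The cost is protocol wording plus at most 28 extra contacts by existing staff. No visit, test or dose changes. Some men will not be reached, and the report will then show how many.

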### Risk of Genvoya®

Genvoya® is a combination anti-HIV medication that contains the drugs tenofovir alafenamide, emtricitabine, elvitegravir, and cobicistat. Based on clinical trials previously conducted of Genvoya®, the drug showed to be well tolerated (see package insert). According to participants, the most common side effect shown was nausea with diarrhea being the second most common side effect. Of those who reported this adverse event, 0.9% and 1.5 % discontinued treatment regardless of the severity (see package insert). Adverse events associated with Genvoya® can include a transient decrease in renal function and slight decreases in bone mineral density. There is also a possibility of lactic acidosis, which can be hard to identify during early stages. These effects occur with prolonged use of the medication and are not expected to occur with the limited 2-day dosing in this protocol.

Genvoya® can also cause flare-ups in those who have hepatitis B virus. It can cause the Hepatitis B virus to suddenly return in a worse form than before if treatment was provided (see package insert). For this reason, it is important that participants not participate in the study if they are known to have Hepatitis B. Nonetheless, the maximum 2 day dosing regimen for this study is unlikely to cause flare-ups in Hepatitis B even if not diagnosed.

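### Short-lived Grade 1-2 nausea, vomiting, diarrhea, headache and rash are kept out of the AE record, so the by-group safety summaries will understate side effects and overstate tolerability of the two doses

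*Combined protocol and SAP*

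**What the plan says.** **Reporting rule.** The section Adverse Event Monitoring and Reporting opens with expedited reporting of AEs of Grade 3 or above. A separate paragraph then names five effects (nausea, vomiting, diarrhea, headache, rash) and states: "The following side effects will not be reported as an AE unless it increases in severity or becomes prolonged beyond the two day study" follow-up after the final biopsy or procedure visit. A list follows, one line per effect, in the form "Nausea: Report if severity is a Grade 3 or higher".

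**Documentation rule.** Under AE Reporting, an event told to the investigators by the participant, or "by medical staff caring for the subject and which meets the criteria will be documented". Monitoring at every visit is specified there for SAEs and unanticipated problems.

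**Use of the data.** Data Safety Monitoring has the investigators review "Summaries of adverse events (Grades 3 or 4), and targeted AEs across study groups". The independent Medical Safety Monitor receives AEs and SAEs by study group. Targeted AEs are not defined.

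**Expected effects.** The section on the risk of Genvoya says "the most common side effect shown was nausea with diarrhea being the second most common side effect".

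**Case report forms.** Under Subject Privacy and Data Confidentiality, the CRF source list reads: "These data will be collected from the screening clinical assessment, the study entry physical examination and screening laboratory tests, and rectal biopsy visits". The sentence before it mentions further clinical data from a study visit, in the singular, without saying which visit.

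**The concern.** A threshold for expedited reporting and a threshold for recording are different things, and here they have been merged. If the five effects are removed from the AE record below Grade 3, the by-group summary is filtered before anyone reviews it. A clean table could then reflect good tolerability or simply the filter, and the reader could not tell which.

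Two further uses of the data suffer:

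- **Relatedness.** The protocol's definition of a probably related event relies on timing and on recurrence at re-challenge. The clinic dose follows the home dose by 24 hours and is in effect a re-exposure, so that judgement needs any event after the first dose to be on record.
- **Drug levels.** Vomiting soon after a dose may affect how much drug is absorbed. Biopsy groups close at four completers, so one undocumented case matters when tissue levels are interpreted.

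**Working it through.** The plan gives no AE rate and no safety sample size, so there is no stated figure to reproduce. The check is a reading of the rules, plus some counting.

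**1. Is this only an expedited-reporting rule?** The opening sentence already sets Grade 3 for expedited reporting of all AEs. If the list of five meant the same thing, it would add nothing. The sentence above the list says these effects are not reported as AEs at all unless an exception applies, and AE Reporting then documents only what meets the criteria. I take those criteria to be the ones just set out, since no others are given.

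**2. Do the sentence and the list agree?**

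| Event among the five | Sentence | List |
|---|---|---|
| Grade 1-2, transient, not worsening | not reported | not reported |
| Grade 1-2, lasting beyond follow-up | reported | not reported |
| Grade 1 rising to Grade 2 | reported, read literally | not reported |
| Grade 3 or higher | reported, if severity has increased | reported |

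The first row is the gap. The second is a plain contradiction, and the third is the same contradiction on a literal reading.

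**3. Is the prolongation test the same in every arm?** Take the final procedure visit as the last specimen visit, and count hours from the home dose: 24 to the clinic dose, plus time to the last visit, plus 48.

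- Arm D: 24 + 8 + 48 = 80 h
- Arm A: 24 + 48 + 48 = 120 h
- Arm B: 24 + 72 + 48 = 144 h
- Arm C: 24 + 96 + 48 = 168 h

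The same low-grade nausea, lasting 100 hours from the home dose, would count as prolonged in Arm D and not in Arms A to C. The only follow-up call with a set time is 24 to 48 hours after the biopsy, and it asks about procedure-related events. In subgroups A.1, B.1 and C.1 (3 x 4 = 12 of the 28 planned dosed completers) the biopsy is at visit 4, so no call is tied to visit 5.

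**4. How many men are involved?** Planned completers: 3 pre-drug + 3 x 8 in Arms A to C + 4 in Arm D = 31, which matches the protocol. Dosed completers: 31 - 3 = 28. Dosed places: 62 - 6 = 56, a ceiling because groups close early. Assumed proportion with a transient Grade 1-2 listed effect: 5% to 20%.

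- Of 28: 28 x 0.05 = 1.4; 28 x 0.20 = 5.6
- Of 56: 56 x 0.05 = 2.8; 56 x 0.20 = 11.2
- Chance of at least one such man among 28: 1 - 0.95^28 = 0.76; 1 - 0.80^28 = 0.998

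**5. What if the CRF source list is exhaustive?** Clinic visits from visit 3 on, all after the home dose: 24 men x 3 + 4 men x 2 = 80. Biopsy visits among them: 28. Not named as a source: 80 - 28 = 52, or 65%. This holds only on the narrow reading of that sentence.

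**6. Weight of one case.** One man in a biopsy group of four is 1/4 = 25% of that tissue time point.

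**The case against.** The strongest reply is that the trial's stated goal is pharmacokinetics and tissue distribution. It sets no tolerability endpoint, uses an approved product for two doses, and discloses the filter openly. That stands, and it limits the consequence. It does not rescue the by-group summaries, which the plan itself promises and which would be biased in a known direction.

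Four stronger readings are tempting, and the documents do not support them.

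- **Nothing below Grade 3 will exist anywhere.** The rule governs what is reported and documented as an AE. It has exceptions for worsening and prolongation, and progress and nurses' notes are listed elsewhere as reviewable records. Rash is also asked about at study visits among the signs of acute HIV infection. That query serves another purpose and does not list nausea, vomiting, diarrhea or headache.
- **Dosing and non-biopsy visits have no form.** The source list sits in a confidentiality section, and the adjoining sentence is open to a wider reading. The visit 3 dose time must be recorded, which suggests the list is not complete. Ambiguity is all that can be claimed.
- **The safety table will show zero drug effects.** Events of Grade 3 or higher, and AEs outside the five, would still appear.
- **Short-term tolerability is the rationale for two doses.** The protocol motivates short courses by the difficulty of adhering to long regimens.

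**Conclusion.** The point holds in limited form and should be fixed. By the plan's own rules, transient Grade 1-2 cases of the five effects are neither reported nor documented as AEs, so the safety summaries will understate side effects and overstate tolerability. Separately, the sentence and the list conflict on prolonged low-grade events, targeted AEs have no definition, and CRF coverage of dosing and non-biopsy visits is unclear.

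The size is uncertain. The figure of 1.4 to 5.6 of 28 dosed completers rests entirely on the assumed 5% to 20%, and the 65% of visits applies only if the CRF source list is exhaustive. The direction of the bias depends on neither. The consequence is confined to the safety reports, any later statement about tolerability, and the reading of drug levels when vomiting follows a dose. A reader should not infer that a stated endpoint of the trial is compromised.

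**What to change.** 1. Keep the Grade 3 threshold for expedited reporting, and say that it applies to expedited reporting only.
2. Record all grades of the five effects on the CRF, with onset time relative to each dose, at every visit after the first dose and at the post-biopsy contact.
3. Reconcile the sentence on worsening and prolongation with the Grade 3 list beneath it.
4. In Data Safety Monitoring, define targeted AEs as these five effects at all grades.
5. Reword the CRF source sentence so that it covers all study visits.

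The cost is a wording amendment and a short form at visits that already take place, with a little more data entry and a less favourable AE table. Doses, sample size and visit schedule are unaffected. If the sponsor prefers not to collect these data, the minimum is to make changes 3 to 5, with targeted AEs defined to match what is collected, and to state that no tolerability conclusion below Grade 3 will be drawn. That would still leave vomiting near a dose undocumented.
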